## 10.4. Serious Adverse Advents (SAE) reporting in UNiTY

For all SAEs, the PI or delegate must do one of the following:

- Record safety reporting-exempt SAEs in the medical notes but not report them to the trials office on an SAE form as per Section 10.4.1 Serious Adverse Events not requiring reporting to the Trial Office.
- 2. **Report SAEs to the trial office in a non-expedited manner**. This can only be done for the predefined subset of SAEs as per Section 10.4.2 Serious Adverse Events requiring non-expedited reporting to the Trial Office.
- 3. **Report SAEs to the trial office in an expedited manner** (within 24 hours of the site research team becoming aware of the event). All SAEs not covered by the above 2 categories must be reported as per Section 10.5 SAE Reporting process.

**Note**: when an SAE occurs at the same hospital at which the participant is receiving trial intervention or is being followed up for trial purposes, processes must be in place to make the trial team at the hospital aware of any SAEs, regardless of which department first becomes aware of the event, in an expedited manner.

### 10.4.1. Serious Adverse Events not requiring reporting to the Trial Office

At whatever time they occur during an individual's participation, from commencement of intervention up to 60 days after the cycle outcome is known, only serious and related SAEs will be reported to the trial office. SAEs that do not fall into these categories will be recorded on follow up CRFs.

All events which meet the definition of serious must be recorded in the participant notes, including the causality and severity, throughout the participant's time on trial, including follow-up, but for trial purposes these events do not require reporting on the SAE Form. Such events are "safety reporting exempt". They will be recorded on the treatment CRFs as part of trial follow-up.

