The trial protocol will not alter local practice for IVF, which will be variable across the centres, as this is a pragmatic trial and reflects what would occur in current treatment. As IUI is not a standard / routine current treatment, this will be subject to more standardisation in-line with the findings from the Cochrane review (16) and global recommendations from the World Health Organisation Human Reproduction Programme (the United Nations Development Programme /United Nations Population Fund /World Health Organisation /World Bank Special Programme of Research, Development and Research Training in Human Reproduction) team who studied this question (17) [MRC/NIHR framework, core element 1: context].

Assessing and quantifying male factors is clearly a critical step in defining infertility as 'unexplained' and as such determining suitability for an IUI intervention. However, there is a lack of evidence defining the lower parameters of semen quality which should be used for couples undergoing IUI. Cohlen et al. conducted a RCT comparing stimulated IUI outcomes and found that it significantly increased live birth rates in couples with a total progressively motile sperm concentration >10 m/ml, but not in couples with total motile sperm concentration <10 m/ml (18).

The criteria for offering stimulated IUI vs. IVF to couples will therefore be: UEI of  $\geq$ 24 months, with the partner providing sperm having a total progressively motile sperm count of >10M (categories A + B), with at least 3% morphological normal forms (17).

Diagnosis of the partner providing sperm underlies suitability for an IUI approach and qualification for the trial, but we know that worldwide (and more-specifically in the UK) that this has great variability (19) so, the need for standardised quality assurance (QA) in assessment of the partner providing sperm is well known. We will therefore run a careful QA system for these observations across the lab teams at participating sites to characterise the variance occurring in assessments (see Section 16.2). This evaluation is fundamental to understanding future application and interpretation of the trial outcome as the single biggest weakness identified in most fertility trials involving male factors (20), it will also enable assessment of emergent technologies highlighted by the World Health Organisation (WHO) as of potential diagnostic value (21, 22) [MRC/NIHR framework, core element 1: context].

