### 6.5. Blinding

Due to the differing natures of the intervention, it is impossible to blind either the care providers, investigators or participants to their allocated group. While we cannot completely rule out some element of behaviour change (and hence performance) bias due to knowledge of allocated interventions, we expect the extent of such bias to be relatively small given the nature of the treatments. We have a strict, objective primary outcome, so we do not expect detection bias to be a factor.

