### 10.ADVERSE EVENT REPORTING

## 10.1. Definitions

Table 2: Adverse event reporting definitions

Severity Definitions	Mild	Awareness of signs or symptoms that do not interfere with the participant's usual activity or are transient and resolved without treatment and with no sequelae.
	Moderate	A sign or symptom, which interferes with the participant's usual activity.
	Severe	Incapacity with inability to do work or perform usual activities.
Adverse Event	AE	Any untoward medical occurrence in a participant participating in the trial which does not necessarily have a causal relationship with the intervention received.
Related Event	RE	An event which resulted from the administration of any of the research procedures.
Serious Adverse Event	SAE	An untoward occurrence that:
		Results in death
		Is life-threatening*
		Requires hospitalisation or prolongation of existing hospitalisation
		Results in persistent or significant disability or incapacity
		Consists of a congenital anomaly/ birth defect
		Or is otherwise considered medically significant by the Investigator**
Unexpected Event	UE	The type of event that is not listed in the protocol as an expected occurrence.
Related and Unexpected Serious Adverse Event	-	A SAE that meets both the definition of a Related and Unexpected Event.

\* The term life-threatening is defined as diseases or conditions where the likelihood of death is high unless the course of the disease is interrupted.

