## 10.3. Adverse event reporting in UNiTY

The reporting period for AEs in UNiTY will be from the day the trial intervention starts until 60 days after the cycle outcome is known. For an unsuccessful cycle (i.e. biochemical pregnancy was not detected) SAEs should be reported for 60 days following the negative pregnancy test. For cycles resulting in pregnancy, SAEs should be reported for 60 days after the pregnancy outcome is known (i.e. live birth, still birth, termination or miscarriage). SAEs should only be reported for trial related treatments, with the exception of the first IVF cycle in the IUI arm. Any non-trial treatment related SAEs should be recorded in the medical notes but not reported to the trial office.

The safety profile for the trial population and interventions are well established, so although it is recommended that the severity, seriousness, and causality of all AEs for both participants and offspring should be recorded in the relevant medical notes, a strategy of targeted reporting of AEs will not affect the safety of participants. Related AEs will be captured as complications within the primary and secondary outcome measures. Only serious, related, and unexpected adverse events, beyond the routine expectations and known risks for fertility treatment, will be reported as SAEs.

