### 14.2.2. Secondary outcomes

The secondary outcomes that are binary (i.e., yes/no) will be analysed using the same methods as described for the primary outcome (see Section 14.2.1), with corresponding 95% confidence intervals (this includes the longer-term assessment at 25 months). For those secondary outcomes that are continuous (e.g. Gestational age at delivery, Birthweight, CSQ-8 score), mixed effects linear regression methods will be utilised to calculate an adjusted mean difference and 95% confidence interval. Time-to-event outcomes (e.g. TTP leading to a live birth) will be analysed using a mixed effects ('frailty') Cox Proportional Hazard model, allowing the same minimisation variables as fixed effects and randomising centre as a random effect. The treatment effect will be expressed as adjusted hazard ratio with 95% confidence interval. Regarding safety, the total number of participants experiencing SAEs will be given by allocation group along with a descriptive table of the events, and statistical significance will be determined by a chi-square test; other safety data including complications will be tabulated by group but are not expected to be formally analysed.

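### Section 14.2.2 does not say which SAEs enter the chi-square test; if reported SAEs are used, the arm comparison depends on unblinded causality judgements made under inconsistent definitions

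*Protocol*

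**What the plan says.** **Analysis.** Section 14.2.2 says that "the total number of participants experiencing SAEs will be given by allocation group along with a descriptive table of the events" and that "statistical significance will be determined by a chi-square test". Other safety data, including complications, are to be tabulated and are not expected to be formally analysed. The section does not define the set of SAEs that is counted.

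**Reporting.** Section 10.3 says: "Only serious, related, and unexpected adverse events, beyond the routine expectations and known risks for fertility treatment, will be reported as SAEs". Section 10.4.1 says that "only serious and related SAEs will be reported to the trial office", and continues: "SAEs that do not fall into these categories will be recorded on follow up CRFs". Section 10.4.3 requires the SAE form for all serious and related events. Section 10.4.2 sends OHSS admissions to the relevant CRFs without expedited reporting.

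**Definition of related.** Section 10.1 gives "An event which resulted from the administration of any of the research procedures". Section 10.5.1 instead grades causality against the intervention and treats possibly, probably and definitely as related.

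**Who judges.** The site PI or a medically qualified delegate assigns causality (10.5.1). The CI or a delegate then reviews the SAE forms received. Section 6.5 says that "it is impossible to blind either the care providers, investigators or participants to their allocated group".

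**Status of the treatments.** Section 1.1.4 says of the comparator: "The trial protocol will not alter local practice for IVF". It describes IUI as not currently routine.

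**The concern.** A comparison of event counts between arms is valid only if events are ascertained alike in both. Here the reporting rules place a causality judgement between the event and the SAE form. That judgement is made by staff who know the allocation, and its formal definition refers to research procedures. A site reading section 10.1 literally could call an admission after routine IVF a consequence of ordinary care, and the same admission after IUI a consequence of the research. A site that regards IVF as the riskier treatment could lean the other way.

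Section 6.5 discounts detection bias because the primary outcome is objective. That argument does not extend to causality attribution.

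The SAE comparison is the only one among SAE and complication data with a planned significance test. Comparing complication rates is secondary objective 3 (section 2.2.1), and lower risk is one of the stated attractions of IUI (section 1.1.4). A p-value here will be read as evidence on relative safety.

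**Working it through.** **Step 1: which events can reach the test?** The sections compare as follows.

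| Section | What it does with a serious event |
|---|---|
| 10.1 | Defines an SAE without any causality condition |
| 10.3 | Reported as an SAE only if related and unexpected |
| 10.4 | SAE is exempt, non-expedited or expedited; anything not in the first two groups is expedited. Exempt events go in the medical notes |
| 10.4.1, first paragraph | Reported only if related; others go on follow-up CRFs |
| 10.4.1, second paragraph | Serious events need no SAE form and go on treatment CRFs |
| 10.4.2 | OHSS admissions go on CRFs |
| 10.4.3 | All serious and related events go on the SAE form |
| 14.2.2 | Tests participants with SAEs; set not specified |

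Sections 10.3, 10.4.1 (first paragraph) and 10.4.3 all require relatedness for reporting. Section 10.3 uses the words 'reported as SAEs', and 14.2.2 separates SAEs from other safety data. The natural reading is therefore that the test counts reported SAEs. An all-cause count is also possible, and the text does not settle the matter.

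**Step 2: arm size.** The protocol gives 942 couples, 471 per arm (Trial Summary). Section 14.1 uses 28% in both arms, a 10-point margin, one-sided alpha 0.025, 90% power and 10% loss:

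n = (1.960 + 1.282)² × 2 × 0.28 × 0.72 / 0.10² ≈ 424 per arm; 848 / 0.90 = 942.2.

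This reproduces the stated 942. No stated figure is in dispute.

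**Step 3: effect of unequal attribution.** The protocol gives no SAE rate, no share judged related and no test level. All three are assumed here; the level is two-sided 5%. If the true rate is s in both arms and shares a and b are judged related, the counted rates are s·a and s·b. The rejection probability of the uncorrected chi-square test is approximately

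Φ[(|p1 − p2| − 1.96·SE0) / SE1], with SE0 = √(2p̄(1 − p̄)/n) and SE1 = √((p1(1 − p1) + p2(1 − p2))/n).

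Worked case: the true related-SAE rate is 4% in both arms and half the IVF-arm events are called unrelated, so p1 = 0.04, p2 = 0.02, n = 471. SE0 = √(2 × 0.03 × 0.97/471) = 0.01112. SE1 = √((0.0384 + 0.0196)/471) = 0.01110. Then (0.02 − 0.02179)/0.01110 = −0.16 and Φ = 0.44. Exact binomial enumeration also gives 0.44.

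| True related-SAE rate, both arms | Half of IVF events re-attributed | A quarter re-attributed |
|---|---|---|
| 3% | 0.34 | 0.11 |
| 4% | 0.44 | 0.13 |
| 6% | 0.61 | 0.18 |

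Varying the share judged related in both arms (IUI/IVF), by exact enumeration with 471 per arm:

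| True SAE rate, both arms | 50/50 | 60/40 | 70/30 | 80/20 |
|---|---|---|---|---|
| 2% | 0.04 | 0.08 | 0.21 | 0.45 |
| 5% | 0.05 | 0.17 | 0.51 | 0.87 |
| 10% | 0.05 | 0.29 | 0.82 | 0.99 |

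With equal shares the test holds its level. With 424 per arm, the 5% row for the unequal splits becomes 0.15, 0.47 and 0.83.

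**Step 4: masking.** With true rates of 5% (IUI) and 10% (IVF) and every serious event counted, power is 0.84. If 80% of IUI events and 40% of IVF events are judged related, the counted rates are 0.05 × 0.8 = 4% and 0.10 × 0.4 = 4%, and the rejection probability falls to 0.05.

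**The case against.** **The test is not stated to be restricted to related events.** Section 14.2.2 does not limit it to SAE-form events, section 10.1 defines an SAE without regard to cause, and section 10.4.1 sends the remaining events to CRFs. A statistical analysis plan, not shown here, could define the set. This stands: a reader might infer that the protocol counts only related SAEs, and it does not say so. But every reporting rule that limits SAEs requires relatedness, and nothing excludes the attribution-dependent count.

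**An arm-specific filter is not shown.** Section 7.1 calls both strategies interventions, 7.1.2 places IVF under the trial intervention, and the one predefined expected SAE, OHSS admission, arises from what section 1.1.2 calls the main risk of IVF. The rule in 10.5.1 refers to the intervention and counts even possibly related events. This also stands. A reader might infer that IVF events are systematically called unrelated; the documents make unequal attribution plausible but do not establish it.

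**There is a second causality review.** The CI reviews causality, cannot downgrade the PI's assessment, and is replaced by an independent reviewer when also the reporting PI. This is a partial safeguard: an event that the site calls unrelated and does not submit never reaches it.

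**Safety does not rest on this test alone.** The complications itemised in 8.2.2.1 carry no relatedness condition. Multiple pregnancy, miscarriage and stillbirth are secondary outcomes estimated with confidence intervals. Section 14.2 treats all secondary outcomes as exploratory. This limits the consequence, although the SAE test alone carries an explicit statement about significance.

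**An all-cause count brings its own imbalance.** Section 8.2.2.1 collects complications for 30 days for each of up to three IUI cycles and 60 days for the first IVF treatment. Section 10.3 runs to 60 days after each cycle outcome is known and includes the first IVF cycle in the IUI arm. This stands and shapes the fix.

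**Conclusion.** The point holds in a conditional form. The protocol plans a significance test on SAEs by arm without saying which SAEs enter it. Its reporting rules make an SAE depend on an unblinded judgement of relatedness, which is defined in two different ways. If reported SAEs are tested, unequal attribution alone could produce or conceal a difference.

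The direction and size are unknown. Under the assumed rates and shares above, the false-positive probability runs from about 0.08 (2% SAE rate, 60/40 split) to 0.99 (10%, 80/20); the 4% against 2% case gives 0.44. These figures show sensitivity and are not forecasts, since the protocol supplies neither SAE rates nor attribution shares. They do not support concluding that the SAE comparison will be biased, or biased in favour of either arm.

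The change should be made: it is inexpensive and removes the dependence on the causality judgement.

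**What to change.** - **Section 14.2.2:** base the between-arm comparison on participants with any serious event irrespective of causality. Combine SAE forms with the serious events that 10.4.1 and 10.4.2 place on CRFs. Count them over the same period from randomisation in both arms, and give a risk difference with a 95% confidence interval. Show related SAEs by arm descriptively, without a p-value.
- **Section 10.1:** define related as related to the allocated fertility treatment in either arm, and use the same wording in 10.5.1.
- **Sections 10.3 to 10.4.3:** reconcile the reporting rules so that every serious event not reported on the SAE form reliably reaches a CRF and is not left only in the medical notes.

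The cost is wording in these sections, one additional derivation, mainly from forms already in use, and a check that those forms cover the common period in both arms. There are two drawbacks. The all-cause count will include unrelated pregnancy admissions, which add noise. It will also differ between arms for reasons unrelated to harm if the collection windows are not aligned, so the common period is essential.

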## 10.4.2. Serious Adverse Events requiring non-expedited reporting to the Trial Office

As the safety profile of the interventions are well established, the causal relationship between the intervention (or the participant's underlying condition), and the SAE, may be known. That is, such events are protocol-defined as "expected" (see Section 10.5.2 Assessment of expectedness of an SAE by the CInvestigator (CI)).

Such events should still be recorded by the trial team in the participant's notes and reported to the Trial Office on the relevant CRFs, but do not require expedited reporting (i.e. immediately on the site becoming aware of the event) since the assessment of expectedness for the specified events has been pre-defined. This includes:

Hospital admissions due to OHSS

This information should be uploaded onto the trial database within four weeks of the event.

## 10.4.3. Serious Adverse Events requiring expedited reporting to the Trial Office

All serious and related AEs must be reported to the Trial Office on a trial specific SAE form within 24 hours of the site research team becoming aware of the event.

### **10.5. SAE Reporting process**

On becoming aware that a participant has experienced an SAE which requires reporting on an SAE form, the PI or delegate should report the SAE to their own Trust in accordance with local practice and to the Trial Office as per the requirements of protocol section 10.4.

To report an SAE to the Trial Office, the PI or delegate must complete, date and sign the trial specific SAE form on the REDCap database. Any other relevant, appropriately anonymised, data should be submitted to the Trial Office using the information below in accordance with the timelines given in Section 10.4.2 and 10.4.3.

## To report an SAE, submit the SAE Form to the UNITY trial team via the main trial database.

Where an SAE Form has been completed by someone other than the PI initially, the SAE form must be countersigned by the PI to confirm agreement with the causality and severity assessments.

On completion of an SAE form, the database will assign a unique SAE reference number and notify the site and Trial Office via email as proof of receipt. The site and the Trial Office should ensure that the SAE reference number is quoted on all correspondence regarding the SAE and filed with the SAE in the ISF. The original SAE form should be updated with any relevant follow-up information.

If the site has not received confirmation of receipt of the SAE or if the SAE has not been assigned a unique SAE identification number within 1 working day of reporting, the site should contact the Trial Office.

## 10.5.1. Assessment of causality of an SAE

When completing the SAE form, the PI (or, throughout this section, a medically qualified delegate) will be asked to define the nature of the seriousness and causality (relatedness; see **Error! Reference source not found.**) of the event.

In defining the causality, the PI must consider if any concomitant events or medications may have contributed to the event and, where this is so, these events or medications should be reported on the SAE form. It is not necessary to report concomitant events or medications which did not contribute to the event.

Table 3: Categories of causality

Category	Definition	Causality
Definitely	There is clear evidence to suggest a causal relationship, and other possible contributing factors can be ruled out.	
Probably	There is evidence to suggest a causal relationship, and the influence of other factors is unlikely.	Related
Possibly	There is some evidence to suggest a causal relationship. However, the influence of other factors may have contributed to the event (e.g., the participant's clinical condition, other concomitant events or medication)	
Unlikely	There is little evidence to suggest there is a causal relationship. There is another reasonable explanation for the event (e.g., the participant's clinical condition, other concomitant events or medication).	Unrelated
Not related	There is no evidence of any causal relationship.	

As per Table 4, all events considered to be 'possibly', 'probably', or 'definitely' related to the intervention will be reported by the trial office as 'related'; all events considered at site to be 'unlikely' or 'unrelated' to the intervention will be reported by the trials office as 'unrelated'. The same categorisation should be used when describing AEs and protocol-exempt SAEs in the participant's medical notes. On receipt of an SAE Form, the Trial Office will forward it, with the unique reference number, to the Chief Investigator (CI) or delegate(s) who will independently review the causality of the SAE on behalf of the Sponsor. Where the CI is also the reporting PI an independent clinical causality review will be performed. An SAE judged by the PI or CI or delegate(s) to have a reasonable causal relationship ("Related" as per Error! Reference source not found.) with the intervention will be regarded as a related SAE (i.e., SAR). The severity and causality assessment given by the PI will not be downgraded by the CI or delegate(s). If the CI or delegate(s) disagrees with the PI's causality assessment, the opinion of both parties will be documented, and where the event requires further reporting, the opinion will be provided with the report.

